## 2.3 Potential Modifiers of Rotavirus Infection, Vaccine Response and Shedding and Intussusception

### **Age-Dependent Susceptibility to Rotavirus Disease and Intussusception**

Severe rotavirus disease occurs most commonly in infants younger than 24 months. The onset of severe rotavirus disease has been reported to coincide with the decline of maternal IgG antibody titers. In addition, we have found a decreased antibody response to the live rotavirus vaccine RV1 in pre-licensure studies in infants with higher levels of transplacental neutralizing antibody to the vaccine strain (unpublished results). Therefore, early protection from rotavirus disease including asymptomatic neonatal rotavirus infections may be due, at least partially, to protection by transplacental antibody that may persist for the first months of life. The risk of intussusception increases with age and many felt the risk of RRV-TV-associated intussusception also increased with age. Therefore, in order to best understand potential mechanisms associated with intussusception and rotavirus vaccines, ideally, it would be important to examine responses in children with the broadest age range possible. Since the age recommendations for the first dose of rotavirus vaccine is 6 weeks to 14 weeks, 6 days, the prospective study will be limited to that age group. We have selected the age range of 6 week to 13 weeks (12 weeks, 6 days) in order to provide assurances that the other 2 month old vaccines can be given on schedule.

### **Breast Milk-Rotavirus Susceptibility and Rotavirus Vaccine Response**

The role of breast milk and rotavirus susceptibility and rotavirus vaccine response is unclear. Two studies found that the highest incidence of rotavirus-associated diarrhea is in children aged 4 to 6 months, suggesting that risk for rotavirus infection increases at the age when weaning from breast-feeding began. Other studies have shown breast-feeding to be associated with protection against symptomatic rotavirus infections. Unfortunately, there are limitations in study design, as other factors such as the presence of maternal antibody or lack of opportunity for exposure were not examined. However, one study specifically supported the role of human milk and factors other than breast milk antibody in protection against rotavirus infection, demonstrating that infants who received human milk with higher concentrations of the glycoprotein lactadherin were more likely to have asymptomatic rotavirus infections compared with those receiving milk with lower concentrations. Since both licensed vaccines are live-attenuated vaccines, there is also a concern that breast milk could play a role in limiting the response to rotavirus vaccination which would impact protection but also the pattern of cytokine response after vaccination. While sub analyses in studies of RV1 and RV5 did not show a decreased efficacy in breastfed infants, the immune response and protection provided by live oral rotavirus vaccines are less in resource poor countries, where nearly all infants were breastfed, than in developed countries. It has been speculated that this could at least in part be due to breast milk antibody and other constituents limiting the replication of the vaccine strains as the levels of antibody are higher in women in resource poor countries. However, more recent data have not found this to be true. To our knowledge there are no data describing differences in vaccine virus shedding, cytokine responses or intussusception in breastfed and non-breastfed infants. In the case-control study evaluating intussusception and RRV-TV, data were re-analyzed to assess risk factors for intussusception unrelated to RRV-TV. Cases were infants who had intussusception between November 1998 and June 1999. Controls were matched by age and hospital of birth. Sociodemographic and feeding practice data were collected through parent and provider interviews. Risk factors for intussusception were identified while controlling for exposure to RRV-TV. Of the 429 cases enrolled, 87% had not received RRV-TV. There were 1763 controls. In addition to finding male sex, Hispanic or black race/ethnicity, and Medicaid enrollment to be factors associated with intussusception, an interaction was found between introduction of solid food and type of formula consumption. Using breast milk as the referent group, infants with introduction of solid food for at least 5 weeks who consumed soy milk-based formula had a lower risk (OR 0.26; 95% CI 0.1-0.7) and infants without introduction of solid food who consumed cow's-milk formula had an increased risk (OR 2.33; 95% CI 1.4-3.9).

Another case control study which studied idiopathic intussusception found that, compared with non-breast-fed infants, breast-fed infants had a relative risk of intussusception of 6.0 (95% CI, 1.8 to 20.4) when breast-feeding at admission was exclusive and of 2.3 (95% CI, 0.8 to 6.6) when it was partial. They concluded that exclusive breast-feeding may be a risk factor for intussusception in infancy.

### **FUT2 Secretor Gene and Rotavirus Susceptibility**

Recently, we and others have reported that, similar to norovirus, risk of rotavirus infection is determined in part by an individual's *FUT2* (fucosyltransferase 2) genotype. The *FUT2* (secretor) gene is responsible for producing an enzyme that makes carbohydrate histo-blood group antigens (HBGAs) available on the surface of the gut. The major human rotavirus genotypes (P4, P6, and P8) bind to HBGA that are synthesized by *FUT2* gene enzymes, specifically H type 1, Lewis B or A antigens. Individuals who are homozygous recessive for the *FUT2* (secretor) gene, and are thus known as “non-secretors,” lack these HBGA on their mucosal surfaces, thereby reducing the ability of rotaviruses to bind and infect intestinal epithelial cells. From a collaborative multi-site surveillance study with the CDC New Vaccine Surveillance Network (CDC NVSN), we identified 56 rotavirus-positive cases of acute gastroenteritis (AGE). None of these rotavirus AGE cases had the non-secretor *FUT2* mutation, compared with 23% of healthy controls ( $p < 0.01$ ). Additional surveillance by the same network identified another 120 rotavirus positive cases, and similarly, found that only 2% of the rotavirus AGE cases were *FUT2* non-secretors compared to 23% of healthy controls ( $p < 0.01$ ).

*FUT2* non-secretors are approximately one-quarter of the population and appear to be largely protected not only against rotavirus but also against norovirus, while the majority of the population with *FUT2* secretor genotype appears to convey risk. Thus, the question arises, why is the *FUT2* genotype maintained – what is the benefit? Several lines of investigation suggest that the carbohydrates synthesized by the *FUT2* enzyme have an anti-inflammatory impact on the intestinal tract. The *FUT2* secretor genotype and oligosaccharide made by *FUT2* enzyme favors microbial diversity, and the growth of beneficial, immune-regulatory intestinal microbiota. Conversely, the lack of these carbohydrates in the *FUT2* non-secretor genotype is a risk factor for inflammatory bowel disease (IBD), and functional changes in the microbiota that are accompanied by sub-clinical levels of inflammation in the local intestinal mucosa.

### **Other Routine Immunizations**

Young infants receive multiple immunizations that are associated with elevated blood cytokines and other inflammatory markers. Routine childhood immunizations have been found to be associated with pro-inflammatory cytokine responses, including  $\text{INF-}\gamma$ , IL-5, IL-6, and IL-8. These routine immunizations may therefore contribute to or interfere with the inflammatory response following rotavirus immunization, potentially altering the risk for intussusception.

Therefore it will be important that in two arms of the study infants will receive routine 2 month old immunizations with one of the two recommended rotavirus vaccines (RV5 or RV1) to evaluate the contribution of blood cytokine responses associated with the addition of routine immunizations to rotavirus vaccine and whether there are stool cytokine responses that are associated with routine immunizations with rotavirus vaccine given concurrently. This will provide two arms that reflect “real world” immunization schedule, allowing for the determination of any changes in the outcomes from receiving all the recommended vaccines. The outcomes found in these two arms will be compared to the RV1 and RV5 alone arms.

### 3 Purpose and Objectives

#### 3.1 Purpose

The purpose of this project is to conduct a pilot study to explore potential biological mechanisms for an association between rotavirus vaccines and intussusception.

#### 3.2 Hypothesis

Our hypothesis is that rotavirus vaccines may increase the risk for intussusception by inducing cytokines or other inflammatory responses that affect the anatomy or functional motility of the small intestine and that there will be a relationship between the pattern of the shedding of vaccine strain rotavirus and the anatomy and or functional motility of the small intestine. We also hypothesize that potential factors such as maternal antibody, human blood group antigens and breast milk in breast-fed infants could modify rotavirus vaccine virus shedding and/or inflammation following vaccination.

#### 3.3 Primary and Exploratory Objectives

Primary Objectives:

- 1) to examine the effects of RV1 and RV5 with or without other routine immunizations on gastrointestinal anatomy
- 2) to assess the feasibility of conducting a larger scale study

Exploratory Objectives:

- 1) to examine the effects of RV1 and RV5 with or without other routine immunizations on gastrointestinal motility
- 2) to examine the effects of RV1 and RV5 with or without other routine immunizations on blood and stool cytokines and inflammatory responses, including clinical reactogenicity events
- 3) to assess patterns and level of vaccine virus shedding after RV1 and RV5
- 4) to provide preliminary data assessing associations with the pattern of rotavirus vaccine strain (RV1 and RV5) shedding in the stool and blood, stool cytokine responses, and the anatomy and/or functional motility of the small intestine; and examine other factors such as maternal antibody, breast milk antibody, and human blood group antigens to see if these factors modify these responses
- 5) to compare MRI and ultrasound imaging

#### 3.4 Study Outcome Measures

##### **Intestinal Anatomy and Motility-Use of Magnetic Resonance Imaging (MRI) and Ultrasound (US)**

We have selected magnetic resonance imaging (MRI) for our main imaging study outcome. Ultrasound will also be done and the results obtained will be compared to the MRI results. This will be done because ultrasound is the standard clinical mode of imaging for intussusception and is more readily available in both the US and abroad compared to MRI. In addition, ultrasound was used in previous studies. While ultrasound is a useful modality to assess the presence or absence of intussusception clinically, it has several limitations which make it difficult to assess the bowel serially. Some of the limitations of ultrasound include its lack of standard planes of imaging, lack of reproducibility, operator dependence, and inability to accurately assess motility and to image the entire abdomen. Alternatively, MRI is ideally suited to evaluate both intestinal anatomy and motility to assess for changes pre- and post-immunization with rotavirus vaccines and this is why MRI will be our main imaging study outcome.

##### **Inflammatory Mediators-Blood and Stool Cytokines**

We will measure both blood and stool cytokines pre- and post-rotavirus vaccination. The cytokines chosen include those shown in past studies to be associated with intussusception and others were chosen because of the association with lymphoid hyperplasia. For blood, we will test C-reactive protein as it is

readily available and used clinically. For both blood and stool, we will measure: IL-2, IL-6, IL-7, IL-8, IL-15, INF- $\gamma$  and TNF- $\alpha$ .

### **Rotavirus Vaccine Virus Shedding**

We will use RT-PCR to identify rotavirus vaccine strains, to examine the duration of shedding and to quantitate rotavirus shedding 5 days post-vaccination. We will then assess the correlation of the amount of virus shedding with intestinal anatomy and motility as well as cytokine and inflammatory responses. The Ct values will be examined and categorized as none, low or high for analysis. We chose 14 days to assess the duration of shedding since studies have shown that most vaccine-associated events occur in the first 14 days and shedding becomes less frequent after 14 days. Vaccine virus shedding (qualitative) will be done on all stools collected. In addition, since we will be collecting reactogenicity data for Days 0-14, stool from other days could be evaluated for stool cytokines should the infant have an adverse event either before or beyond the Visit 2 stool evaluation.

### **Potential Modifiers of Rotavirus Infection, Vaccine Response and Shedding and Intussusception Maternal Serum Antibody**

In order to examine the possible role of maternal antibody to rotavirus, we will test the initial blood sample for maternal antibody to see if maternal antibody affects shedding of vaccine virus, blood and stool cytokine responses and intestinal motility and anatomy. In addition, we will measure the infant's IgA antibody to assure that the child has not been infected with rotavirus.

### **Breast Milk Antibody**

We will obtain a breast milk sample from breastfeeding mothers of infants enrolled in the study in order to examine the potential effect of rotavirus IgA in breast milk on vaccine virus shedding, cytokine responses, and intestinal anatomy and motility. The analysis will be exploratory given the small sample size.

### **Secretor Status**

Thus, in an exploratory analysis, we will examine whether there is an association with secretor status and inflammatory response.

## **4 Research Plan**

### **4.1 Overview of Study**

This study is a prospective clinical study designed to 1) examine the effects of RV1 and RV5 alone or with other routine immunizations on gastrointestinal anatomy 2) to assess the feasibility of conducting a larger scale study. Exploratory objectives include 1) to examine the effects of RV1 and RV5 with or without other routine immunizations on gastrointestinal motility 2) to examine the effects of RV1 and RV5 with or without other routine immunizations on blood and stool cytokines and inflammatory responses, including clinical reactogenicity events 3) to assess patterns and level of vaccine virus shedding after RV1 and RV5 4) to provide preliminary data assessing associations with the pattern of rotavirus vaccine strain (RV1 and RV5) shedding in the stool and blood, stool cytokine responses, and the anatomy and/or functional motility of the small intestine; and examine other factors such as maternal antibody, breast milk antibody, and human blood group antigens to see if these factors modify these responses and 5) to compare MRI and ultrasound imaging.

Healthy infants 6-13 weeks of age will be randomized (1:1:1:1) to receive either, RV1 alone, RV5 alone, RV1 with ACIP routinely recommended immunizations (Diphtheria, Tetanus and Pertussis (DTaP), *Haemophilus influenzae* type b (Hib), pneumococcal conjugate (PCV13), Hepatitis B (HBV) and

inactivated polio (IPV)) or RV5 with routine immunizations. Imaging study personnel and parents will be blinded to the rotavirus vaccine type; parents will be informed about the rotavirus vaccine type at the completion of the study. Up to 150 infants will be enrolled (see inclusion/exclusion below). The age-group of infants 6-13 weeks of age was chosen so enrolled infants can receive their first dose of rotavirus vaccine at the AAP/ACIP recommended age of 2 months (minimum age of 6 weeks and maximum age of 14 weeks and 6 days) and, to assure that other ACIP recommended vaccines can be administered at the recommended age.

Recruitment and enrollment will occur prior to the first study visit. There will be three scheduled study visits after recruitment/enrollment. . Infants will be randomized to either RV1, RV1 plus other immunizations, RV5 alone, or RV5 plus other immunizations. Visit 1 (day 0) will include blood, saliva, stool and breast milk collection . The MRI and ultrasound will be performed prior to vaccination. Children will receive the immunizations to which they are randomized. Imaging personnel and parents will be blinded to rotavirus vaccine type; they will be informed about other vaccines administered. A second MRI and ultrasound will be performed at Visit 2 (day 5) and blood and stool samples collected. Parents will be unblinded at the completion of Visit 3 (day 14). Arrangements will be made to get remaining doses of same rotavirus vaccine. Daily stool samples will be collected at home during the 15 day study period (on vaccination day 0 and for next 14 days). A memory aid will be completed to collect reactogenicity data on days 0 and for the next 14 days. Remaining stools and reactogenicity data from parents will be collected at Visit 3. **See Appendix 1 for detailed description of visits and timeline.**

We will assess blood and stool cytokine responses and intestinal anatomy and motility after rotavirus vaccination by comparing pre-vaccination with post-vaccination responses in the study infants. Cytokines and intestinal anatomy and motility will be assessed at baseline (Visit 1, the day of vaccine receipt) and 5 days after vaccination (Visit 2). For both blood and stool, the following cytokines will be tested: IL-2, IL-6, IL-7, IL-8, IL-15, INF- $\gamma$  and TNF- $\alpha$ . Additional biomarkers may be studied. The 5 day period post-vaccination was chosen because this time period corresponds with the peak period for intestinal replication of rotavirus vaccine virus for both vaccines.

In order to protect the health of infants, we will provide procedures to facilitate and assure that infants enrolled in the study will receive the routinely recommended vaccines for 2 month old infants which are DTaP, Hib, PCV13, HBV and IPV that will also allow them to get their 4 month vaccines on schedule.

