letter for their pediatrician. These infants will still be recommended to have a 2-month well child check-up, but will be asked not to receive 2-month vaccines at this visit. Children receiving other childhood vaccines as part of the study will receive the following vaccines Pentacel (DTaP, Hib and IPV combination), Prevnar (PCV13) and HBV, in addition to the rotavirus vaccine. If one of these is not available we will replace it with another equivalent licensed vaccine. All vaccines administered as part of the study will be documented for the parent and child's health care provider. This information will be faxed to the provider. The vaccines administered will be documented in EPIC, in IMPACT (the Ohio State Registry) and in letter form with copies of the EPIC documentation to the parent and provider of the enrolled child.

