## 5.3 Study Visits

### Enrollment/Recruitment Visit

- review inclusion/exclusion criteria and medical history
- obtain informed consent
- obtain a release to get medical information from the primary care provider
- collect contact information including the primary care provider of infant and the date of 2 month check up if known
- if refuses study, record refusal reason on screening log
- sample collection instructions
- distribute sample collection supplies
- review MRI and ultrasound prep
- randomize to study group and inform parent of result of all routine vaccines or rotavirus vaccine alone (not specific rotavirus vaccine type)
- schedule visit 1  
give written instructions for Visit 1 to parent (Appendix 5) **Reminder Call 1 (day prior to Visit 1)**
- review sample collection instructions
- review MRI/ultrasound prep  
review time, date and location of Visit 1 **Visit 1 (Day 0-Vaccine Administration)**
- contact information will be reviewed and updated if necessary
- inclusion and exclusion criteria will be reviewed to determine if child still meets criteria for study
- temperature will be recorded prior to immunization; axillary temperature must be <100.4° F prior to administration of vaccines
- breast milk specimen brought from home if mother is breast feeding or can be collected at the visit if needed
- saliva specimen collected for human blood group antigen testing
- baseline stool specimen (brought from home) before receiving the rotavirus vaccine
- MRI to assess intestinal anatomy and motility
- Ultrasound of abdomen to assess intestinal anatomy
- baseline blood specimen for cytokine testing and maternal antibody testing (IgG)
- The Vaccine Information Sheet (VIS) will be provided to parents/guardians for all vaccines administered.
- The study product administrator, who is licensed to administer the vaccine (e.g., MA, LPN, RN, NP, PA, or MD), will orally administer the rotavirus vaccine as indicated in the randomization code
  - if the infant vomits after receiving the vaccine, in accordance with AAP and ACIP recommendations, the vaccine will not be readministered but time of vaccine administration and vomiting will both be documented.

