## **10 RANDOMIZATION, DATA MANAGEMENT, STATISTICAL PLAN**

### **10.1 Randomization Plan**

Upon meeting the inclusion and exclusion criteria, subjects will be randomized to one of the four vaccine groups: 1) RV1 alone, 2) RV5 alone, 3) RV1 with routine immunizations (DTaP, Hib, PCV13, HBV and IPV) or 4) RV5 with routine immunizations. This will be a simple randomization using SAS® PROC PLAN, which uses a random number generator to make assignments. Study statisticians will generate the assignments in advance of any enrollment. After obtaining informed consent, an unblinded research personnel will contact the statistician to obtain a specific subject's assignment. Parents and all study radiologists will be blinded as to which arm the child is randomized to until completion of the study. Parents will learn which rotavirus the child received at the completion of Visit 3. Parents will be informed about the specific other vaccines used in the study. If there is an urgent medical need to unblind during the study, then this can be done by calling the on call study staff.

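### Section 4.1 lets imaging personnel know which routine vaccines were given while section 10.1 blinds radiologists to arm; the rules conflict, and the primary reading is left open to knowledge of one of the two randomized factors

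*Combined protocol and SAP*

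**What the plan says.** Section 4.1 describes the imaging blind twice. First: "Imaging study personnel and parents will be blinded to the rotavirus vaccine type". Then, in the account of the visits: "Imaging personnel and parents will be blinded to rotavirus vaccine type; they will be informed about other vaccines administered". Both limit the blind to rotavirus type, and the second adds disclosure of the other vaccines, with imaging personnel and parents together as its subject.

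Section 10.1 says something different: "Parents and all study radiologists will be blinded as to which arm the child is randomized to until completion of the study". When it turns to the other vaccines it mentions parents only: "Parents will be informed about the specific other vaccines used in the study". The enrollment visit in section 5.3 also tells only parents whether the infant is in a routine-vaccine arm: "inform parent of result of all routine vaccines or rotavirus vaccine alone (not specific rotavirus vaccine type".

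Section 10.3(b) makes terminal ileum thickness on MRI the primary anatomical outcome and bases the primary between-group comparison on the pre-post change. Section 9.13 has a pediatric radiologist measure the wall at three locations and average them. The only blinding that 9.13 and 9.22 state for anatomic reading concerns a second radiologist, who re-reads a random subset blinded to the first assessment and to time point.

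**The concern.** The four arms form a two-by-two layout: RV1 or RV5, with or without routine vaccines. Knowing the other vaccines reduces four possible arms to two, so it reveals one of the two randomized factors. Section 4.1, read as written, gives imaging personnel that knowledge. Section 10.1 denies it to radiologists. Staff cannot comply with both.

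The outcome depends on a reader's judgement about where and how to measure a thin wall. The semi-automated software is described for motility only, and even there the first reader chooses the bowel segment. Section 2.3 gives readers a reason to look for a difference, because it proposes that routine immunizations may alter the inflammatory response to rotavirus vaccine. The effect with and without routine vaccines is part of the first primary objective, and the section on power says the observed effect sizes will inform later studies. A reading artefact tied to routine-vaccine status would therefore carry forward.

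**Working it through.** **1. The statements side by side.**

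| Place | Imaging staff or radiologists | Parents |
|---|---|---|
| 4.1, design paragraph | blind to rotavirus type | blind to rotavirus type |
| 4.1, visit paragraph | blind to rotavirus type; told other vaccines | blind to rotavirus type; told other vaccines |
| 5.3, enrollment visit | not mentioned | told routine vaccines or rotavirus vaccine alone |
| 9.13 and 9.22, anatomic reading | second reader only: blind to first reading and time point | not mentioned |
| 10.1 | radiologists blind to arm | blind to arm, yet told other vaccines |

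For radiologists, the second and last rows are incompatible. For parents, 10.1 is also inconsistent with itself and with 5.3. No row states what the primary anatomic reader knows about time point.

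**2. Comparisons exposed.** Section 10.3(b) plans six pairwise comparisons. Writing + for routine vaccines:

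- same routine status: RV1 v RV5; RV1+ v RV5+ (2 pairs)
- different routine status: RV1 v RV1+; RV5 v RV5+; RV1 v RV5+; RV5 v RV1+ (4 pairs)

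Four of six are exposed. The four-group F-test that precedes them is exposed too. So is the with-versus-without test that decides whether groups are combined for an RV1 v RV5 comparison. In the combined comparison itself, a shift tied to routine status largely cancels, because 1:1:1:1 allocation roughly balances that status.

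**3. Size of the bias.** Let s_pre and s_post be the mean reading shifts, in mm, in infants known to have had routine vaccines, relative to those known not to have had them. In an exposed comparison:

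expected observed difference in change = true difference + (s_post − s_pre)

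- equal shift on both exams, s_pre = s_post: bias 0
- shift on the post exam only, s_pre = 0: bias s_post
- post-only analysis, which 10.3(b) calls additional: bias s_post whatever s_pre is

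The second case needs the reader to know time point as well as routine status, or to infer it. A larger sample does not reduce the bias.

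**4. Illustration only.** The plan has no power calculation and gives no SD, alpha or reading error, so there is no planned figure to reproduce. Assume a two-sided alpha of 0.05, no true effect, equal arms, and a net shift d = (s_post − s_pre)/SD of the change score. With n = N/4 per arm:

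- one exposed pair: Φ(d/√(2/n) − 1.96) + Φ(−d/√(2/n) − 1.96)
- F-test: noncentral F with 3 and N − 4 df, noncentrality N(d/2)²

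N = 150 is the enrollment ceiling ("Up to 150 infants will be enrolled"), so n = 37.5. N = 105 is 70% of 150, from the MRI benchmark in Appendix 2.

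| d (assumed) | Pair, N=150 | F, N=150 | Pair, N=105 | F, N=105 |
|---|---|---|---|---|
| 0 | 0.05 | 0.05 | 0.05 | 0.05 |
| 0.1 | 0.07 | 0.07 | 0.07 | 0.07 |
| 0.2 | 0.14 | 0.15 | 0.11 | 0.12 |
| 0.3 | 0.26 | 0.30 | 0.19 | 0.21 |
| 0.5 | 0.58 | 0.72 | 0.44 | 0.54 |

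Example, d = 0.3 and N = 150: √(2/37.5) = 0.231, 0.3/0.231 = 1.30, Φ(1.30 − 1.96) ≈ 0.25, and the other tail adds under 0.001, giving 0.255 without intermediate rounding. For the F-test the noncentrality is 150 × 0.15² = 3.375. The table shows what a net shift would do, not that one exists.

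**The case against.** The strongest reply is that section 10.1, the section devoted to randomization, already has the right rule for the people who read the primary outcome, and that it and 5.3 disclose the other vaccines to parents only. The conflict would then rest on a pronoun in an overview, perhaps meant for parents, and on the term imaging personnel, which could mean technologists. Both readings are possible, and if 10.1 is followed the primary MRI reading is protected. But the sentence as written covers both groups, the other statement in 4.1 also stops at rotavirus type, and 9.13 and 9.22 do not break the tie. Nor is 10.1 a secure arbiter, since its rule for parents cannot be kept.

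Three further objections stand and limit the point:

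- A reader might infer that any drift in routine-vaccine infants biases the four comparisons by its full amount. The primary analysis is of change, and a drift equal on both exams drops out.
- A reader might infer thicker walls in the routine-vaccine arms. Section 2.3 says routine vaccines could add to the inflammatory response or interfere with it, so no direction follows.
- A reader might add that "The vaccines administered will be documented in EPIC" gives readers the allocation through the medical record. No section says that readers consult it, and if they did, rotavirus type would be exposed as well. The point does not rely on it.

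**Conclusion.** The conflict is real and should be resolved before images are read. Followed literally, section 4.1 unmasks one of two randomized factors for a reader-measured primary outcome and exposes four of six pairwise comparisons, together with the overall test and the pooling decision. RV1 v RV5 at the same routine status is not exposed by this route.

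The bias in the primary change score is the post-exam shift minus the pre-exam shift: zero if the reader drifts equally on both, the whole post-exam shift if only that exam is affected. The latter is possible because the primary reader is not stated to be blinded to time point. Direction is open and the documents give no size; the error rates above rest on assumed shifts and an assumed alpha.

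The documents do not support the stronger conclusion that the readings will be made unblinded or will be biased. They show two incompatible instructions, one of which would permit it. Pilot status and the absence of a power calculation lower the stakes for formal inference, but not for effect estimates meant to guide later studies.

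**What to change.** State one masking rule and use it everywhere.

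- **4.1, both statements:** parents are told whether routine vaccines are given but not the rotavirus type. All image readers and the post-processing assistant are told neither. The same applies to technologists as far as practicable; parents who know the status accompany the infant to imaging, so full masking there cannot be guaranteed.
- **9.13 and 9.22:** repeat the rule for the primary reader. Also blinding that reader to time point, as is already planned for the second reader, would close the route by which a post-exam shift enters the change score.
- **10.1:** say that radiologists are blinded to the full four-arm assignment and parents to rotavirus type only.
- **Reading procedure:** supply images under study ID, without vaccine information, until readings are locked. Keep the existing routes for urgent unblinding (10.1) and for clinically concerning findings (6.6).

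The cost is small: image coding, a reading-room instruction and wording changes. No extra infants, visits or scans are needed, and the analysis is unchanged.
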